### Document History

| Document          | Version Date  |
|-------------------|---------------|
| Original protocol | 22 April 2022 |

PFIZER CONFIDENTIAL

## 1. PROTOCOL SUMMARY

### 1.1. Synopsis

A Phase 1, Open-Label, Single Dose Study to Investigate the Pharmacokinetics, Pharmacodynamics, Safety, and Tolerability of Ponsegromab Administered Subcutaneously in Healthy Adult Chinese Participants

**Brief Title:** A Phase 1 PK, PD, Safety and Tolerability Study With Ponsegromab Single-Dose Subcutaneously Administered in Healthy Adult Chinese Participants

[figure not shown]
### Rationale

The purpose of this study is to evaluate the PK, PD, safety, and tolerability of ponsegromab following 100 mg and 400 mg single SC dose in healthy adult Chinese participants. Results from this study will be used to inform clinical development of ponsegromab in China, to facilitate China's participation in global pivotal studies, and to support China registration of ponsegromab.

### Objectives and Endpoints

| Objectives  | Endpoints   |
|---|---|
| Primary: 

To characterize the serum PK of ponsegromab following a single SC administered dose in healthy adult Chinese participants.

              | Primary: 

Ponsegromab serum PK parameters (unbound and total), as data permit: <math>AUC_{inf}</math>, <math>AUC_{last}</math>, <math>C_{max}</math>, <math>T_{max}</math>, and <math>t_{1/2}</math>.

 |
| Secondary: 

To evaluate the safety and tolerability of ponsegromab following a single SC administered dose in healthy adult Chinese participants.

 | Secondary: 

AEs, clinical safety laboratory tests, vital signs (blood pressure, pulse rate), physical examinations, and 12-lead ECGs for approximately 18 weeks post single dose.

                     |
| CCT   |   |

PFIZER CONFIDENTIAL

## Overall Design

### Brief Summary

This is an open-label, single dose study to characterize the PK, PD, safety, and tolerability of ponsegromab following 100 mg or 400 mg single SC dose in healthy adult Chinese participants.

### Number of Participants

Approximately 18 participants will be enrolled in this study (N=9 for each cohort) with the goal of attaining approximately 16 participants (N=8 for each cohort) evaluable for the primary endpoints.

Note: “Enrolled” means a participant’s agreement to participate in a clinical study following completion of the informed consent process and screening. A participant will be considered enrolled if the informed consent is not withdrawn prior to participating in any study activity after screening. Potential participants who are screened for the purpose of determining eligibility for the study, but do not participate in the study, are not considered enrolled, unless otherwise specified by the protocol.

### Intervention Groups and Duration

Participants who meet eligibility criteria at baseline will receive a single SC dose of ponsegromab at 100 mg (Cohort 1) or 400 mg (Cohort 2) on Day 1. Participants in the 100 mg cohort will be dosed firstly, and will be kept under safety monitoring for 8 days at the CRU. Progression to 400 mg will occur only if 100 mg is well tolerated after reviewing the safety data up to 8 days post-dose as judged by the investigator. Sentinel dosing may be implemented in the 400 mg cohort as judged by the investigator: eg, 2 participants may be dosed prior to the remaining participants in Cohort 2. If the dose level is determined to have an acceptable safety and tolerability profile up to 8 days post-dose, as judged by the investigator for the first 2 sentinel participants, the remaining 7 participants in that cohort will be dosed. The total duration of each participation in this study is approximately 22 weeks, including a screening period of up to 4 weeks to confirm eligibility and a follow-up period of approximately 18 weeks after the single SC dose.

Participants who discontinue prior to completion of the study for non-safety related reasons may be replaced, at the discretion of the investigator and sponsor study team.

### Data Monitoring Committee or Other Independent Oversight Committee: No

[figure not shown]
### Statistical Methods

All data analyses will be descriptive. The serum PK parameters of ponsegromab (unbound and total) will be listed and descriptively summarized by cohort. **CCI**

For each cohort,

the serum concentrations of ponsegromab (unbound and total) will be listed and descriptively summarized by nominal sampling time and cohort. Within each cohort, individual participant and summary profiles (mean and median plots) of the serum concentration-time

CCI

Safety data (AEs, ECGs, BP, PR, and safety laboratory data) will be presented in tabular and/or graphical format and summarized descriptively by cohort, where appropriate.

## 1.2. Schema

Not applicable.

### 1.3. Schedule of Activities

The SoA table provides an overview of the protocol visits and procedures. Refer to the **STUDY ASSESSMENTS AND PROCEDURES** section of the protocol for detailed information on each procedure and assessment required for compliance with the protocol.

The investigator may schedule visits (unplanned visits) in addition to those listed in the SoA table, in order to conduct evaluations or assessments required to protect the well-being of the participant.

| Day relative to Day 1
For abbreviations, refer to Appendix 7 | Screening | Admit to CRU a
(Day -1) | Inpatient stay at CRU |       |       |       |       |        | Outpatient FU |           |           |           |           |           | ET/DC      |   |
|---|-----------|---------------------------------------|-----------------------|-------|-------|-------|-------|--------|---------------|-----------|-----------|-----------|-----------|-----------|------------|---|
|   |           |                                       | Day 1                 | Day 2 | Day 3 | Day 4 | Day 6 | Day 8  | Day 10 ±1     | Day 15 ±1 | Day 29 ±1 | Day 50 ±2 | Day 71 ±3 | Day 93 ±7 | Day 106 ±7 |   |
| Hours After Dose
(for inpatient portion)                                     |           |                                       | 0                     | 12 ±1 | 24 ±2 | 48 ±2 | 72 ±4 | 120 ±4 | 168 ±4        |           |           |           |           |           |            |   |
| Informed consent  | X         |                                       |                       |       |       |       |       |        |               |           |           |           |           |           |            |   |
| Inpatient stay at CRU   |           | X                                     | →                     | →     | →     | →     | →     | →      | X             |           |           |           |           |           |            |   |
| Outpatient visit to CRU   |           |                                       |                       |       |       |       |       |        |               | X         | →         | →         | →         | →         | →          | X |
| Assessment of eligibility,
medical/medication history c           | X         | X                                     |                       |       |       |       |       |        |               |           |           |           |           |           |            |   |
| Physical exam and weight (plus height
at Screening, only) d       | X         | X                                     |                       |       |       |       |       |        | X             | X         | X         | X         | X         | X         | X          | X |
| Review alcohol/caffeine/tobacco, as
applicable                               | X         | X                                     |                       |       |       |       |       |        | X             | X         | X         | X         | X         | X         | X          | X |
| Review prior or concomitant
treatments, as applicable                        | X         | X                                     | →                     | →     | →     | →     | →     | →      | →             | →         | →         | →         | →         | →         | →          | X |
| Demography  | X         |                                       |                       |       |       |       |       |        |               |           |           |           |           |           |            |   |
| Review contraception use  | X         | X                                     |                       |       |       |       |       |        | X             | X         | X         | X         | X         | X         | X          | X |
| Serious and non-serious AEs
monitoring                                       | X         | X                                     | →                     | →     | →     | →     | →     | →      | →             | →         | →         | →         | →         | →         | →          | X |
| Injection site assessment e  |           |                                       | X                     | →     | X     |       |       |        |               |           |           |           |           |           |            |   |
| Supine 12-lead ECG (triplicate)   | X         |                                       | X f        |       | X     | X     |       | X      | X             |           |           | X         | X         |           |            | X |
| Single, supine BP and PR (triplicate
pre-dose Day 1, only)                   | X         |                                       | X                     | X     | X     | X     | X     | X      | X             | X         | X         | X         | X         | X         | X          | X |
| Eligibility overview for study
enrollment g                       |           | X                                     | X                     |       |       |       |       |        |               |           |           |           |           |           |            |   |
| Study intervention administration   |           |                                       | X                     |       |       |       |       |        |               |           |           |           |           |           |            |   |

PFIZER CONFIDENTIAL

|  | Screening         |   | Inpatient stay at CRU              |       |       |       |       |        | Outpatient FU |           |           |           |           |           | ET/DC      |
|--|-------------------|---|------------------------------------|-------|-------|-------|-------|--------|---------------|-----------|-----------|-----------|-----------|-----------|------------|
|  | Day -28 to Day -2 |   | Admit to CRU a (Day -1) | Day 2 | Day 3 | Day 4 | Day 6 | Day 8  | Day 10 ±1     | Day 15 ±1 | Day 29 ±1 | Day 50 ±2 | Day 71 ±3 | Day 93 ±7 | Day 106 ±7 |
| Day relative to Day 1
For abbreviations, refer to Appendix 7                               |                   |   |                                    |       |       |       |       |        |               |           |           |           |           |           |            |
| Hours After Dose
(for inpatient portion)   |                   |   | 0                                  | 12 ±1 | 24 ±2 | 48 ±2 | 72 ±4 | 120 ±4 | 168 ±4        |           |           |           |           |           |            |
| Blood samples:
serum FSH (females
amenorrheic ≥12 months, only),
HIV, HBsAg, HBcAb, HCVAb,
Syphilis test | X                 |   |                                    |       |       |       |       |        |               |           |           |           |           |           |            |
| Safety laboratory tests h   | X                 | X |                                    |       | X     | X     | X     |        | X             | X         | X         | X         | X         |           | X X        |
| CCI   |                   |   |                                    |       |       |       |       |        |               |           |           |           |           |           |            |
|  |                   |   |                                    |       |       |       |       |        |               |           |           |           |           |           |            |
| Blood Sample (s): serum ponsegromab (PK)   |                   |   | X i                     | X     | X     | X     | X     | X      | X             | X         | X         | X         | X         | X         | X X        |
| Urine drug test  | X                 | X |                                    |       |       |       |       |        |               |           |           |           |           |           |            |
| COVID-19 test(s) j  | X                 |   |                                    |       |       |       |       |        |               |           |           |           |           |           |            |

- Participants will admit to CRU at least 12 hours prior to dosing. Admission procedures to be conducted once, unless deemed necessary by investigator or sponsor.
- FU to approximately 18 weeks postdose planned; FU visits may be adjusted at investigator/sponsor discretion, including to monitor open AE, or based on emerging data (see [Section 4.4](#)).
- Medication history will be updated at each visit.
- Full PE at Screening or admission; at all other timepoints, limited PE performed for findings during previous exam or new/open AEs, at investigator discretion. PE may be conducted at final FU visit, at investigator discretion. Body weight to be measured at all indicated timepoints.
- Injection site assessment at predose (-30 min to 0 h), and 1 h (±10 min), 6 h (±0.5 h), 12 h (±1 h) and 24 h (±2 h) postdose. Additional assessments at investigator discretion and/or until any symptoms resolve. Additional requirements see [Section 8.2.2](#).
- Baseline ECGs should be triplicate collections at 60 min (±5 min) predose, 30 min (±5 min) predose, and 15 min (±5 min) predose (nine measurements in total). Additional requirements on ECGs see [Section 8.2.4](#).
- Eligibility overview for study enrollment could be performed after all procedures are completed on Day -1, or before all procedures on Day 1, according to site operating practices.
- See [Appendix 2](#) for safety laboratory tests in the study.
- Predose sample collection may be conducted between CRU admission and dose administration on Day 1.
- The timing and methods of COVID-19 test(s) should follow the requirements from local regulations or the investigator (CRU).

PFIZER CONFIDENTIAL

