### 3. OBJECTIVES AND ENDPOINTS

| Objectives  | Endpoints   |
|---|---|
| Primary: 
 
• To characterize the serum PK of ponsegromab following a single SC administered dose in healthy adult Chinese participants.
 
              | Primary: 
 
• Ponsegromab serum PK parameters (unbound and total), as data permit: <math>AUC_{inf}</math>, <math>AUC_{last}</math>, <math>C_{max}</math>, <math>T_{max}</math>, and <math>t_{1/2}</math>.
 
 |
| Secondary: 
 
• To evaluate the safety and tolerability of ponsegromab following a single SC administered dose in healthy adult Chinese participants.
 
 | Secondary: 
 
• AEs, clinical safety laboratory tests, vital signs (blood pressure, pulse rate), physical examinations, and 12-lead ECGs for approximately 18 weeks post single dose.
 
                     |
| CCI   |   |

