#### 4.2. Scientific Rationale for Study Design

This study is the first clinical study with ponsegromab in the Chinese population. The study is designed as open-label, with PK in healthy adult Chinese participants as the primary objective. The safety and tolerability **CCI**

██████████ will be investigated as secondary **CCI**

The intended route of administration of ponsegromab to patients is SC; the same route will be tested in this study.

[figure not shown]
As is typical for early development studies, and to allow better comparisons in PK, PD, safety, and tolerability of ponsegromab between Chinese and non-Chinese, the population envisioned for this China Phase 1 study will be similar to that in studies C3651001 and C3651002, ie, healthy male and female participants. Female participants will be confirmed to be categorized as women of non-childbearing potential as, at the present time, embryo-fetal developmental toxicology studies with ponsegromab have not been conducted. In male participants, appropriate measures to minimize potential transfer of ponsegromab via semen to partners are expected to be followed (see [Appendix 4](#)).

Risks to study participants will be minimized by dose administration in an inpatient setting, with careful assessment and on-going review of safety data. After single-dose SC administration, there will be a follow-up period of approximately 18 weeks. This duration has been chosen based on the PK half-life of ponsegromab observed in the completed clinical trials **CCI** ██████████ Clinical safety laboratory tests (see [Section 8.2.5](#)), thorough assessments of vital signs, ECGs, physical examinations, and AE monitoring will provide essential data to evaluate the safety and tolerability of ponsegromab.

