#### **4.4. End of Study Definition**

The end of the study is defined as the date of the last visit of the last participant in the study.

A participant is considered to have completed the study if he/she has completed all periods of the study, including the procedures at their last follow-up visit. Follow-up visits in addition to those in the SoA may be scheduled at investigator discretion, including to monitor open AE, or based on emerging data.

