### **5.3.4. Contraception**

The investigator or his or her designee, in consultation with the participant, will confirm that the participant has selected an appropriate method of contraception for the individual participant and his or her partner(s) from the permitted list of contraception methods (see [Appendix 4 Section 10.4.4](#)) and will confirm that the participant has been instructed in its consistent and correct use. At time points indicated in the schedule of activities ([SoA](#)), the investigator or designee will inform the participant of the need to use highly effective contraception consistently and correctly and document the conversation and the participant's affirmation in the participant's chart (participants need to affirm their consistent and correct use of at least 1 of the selected methods of contraception) considering that their risk for pregnancy may have changed since the last visit. In addition, the investigator or designee will instruct the participant to call immediately if the selected contraception method is discontinued or if pregnancy is known or suspected in the participant or partner.

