#### **8.3.1. Time Period and Frequency for Collecting AE and SAE Information**

The time period for actively eliciting and collecting AEs and SAEs (“active collection period”) for each participant begins from the time the participant provides informed consent, which is obtained before the participant’s participation in the study (ie, before undergoing any study-related procedure and/or receiving study intervention), through and including a

PFIZER CONFIDENTIAL

minimum of the time of the final planned follow-up visit after the administration of the study intervention.

Follow-up by the investigator continues throughout and after the active collection period and until the AE or SAE or its sequelae resolve or stabilize at a level acceptable to the investigator.

For participants who are screen failures, the active collection period ends when screen failure status is determined.

If the participant withdraws from the study and also withdraws consent for the collection of future information, the active collection period ends when consent is withdrawn.

If a participant permanently discontinues or temporarily discontinues study because of an AE or SAE, the AE or SAE must be recorded on the CRF and the SAE reported using the CT SAE Report Form.

Investigators are not obligated to actively seek information on AEs or SAEs after the participant has concluded study participation. However, if the investigator learns of any SAE, including a death, at any time after a participant has completed the study, and he/she considers the event to be reasonably related to the study intervention, the investigator must promptly report the SAE to Pfizer using the CT SAE Report Form.

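### The visit schedule ends at Day 106, 15 weeks after dosing, although the secondary endpoint, design text and SAP state about 18 weeks of follow-up

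*Protocol*

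**What the plan says.** In the protocol's Schedule of Activities (Section 1.3), both copies of the column headings end with "Day 93 ±7 | Day 106 ±7", followed only by an early-termination/discontinuation column. A footnote to the same table says "FU to approximately 18 weeks postdose planned; FU visits may be adjusted at investigator/sponsor discretion".

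Elsewhere the figure is 18 weeks:

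- The synopsis gives total participation as "approximately 22 weeks, including a screening period of up to 4 weeks to confirm eligibility and a follow-up period of approximately 18 weeks"; protocol Section 4.1 and SAP Section 2.3 say the same.
- The secondary endpoint in protocol Section 3, repeated in SAP Section 2.2, covers adverse events, laboratory tests, vital signs, "physical examinations, and 12-lead ECGs for approximately 18 weeks post single dose".
- Section 4.2 gives about 18 weeks and explains it: "This duration has been chosen based on the PK half-life of ponsegromab observed in the completed clinical trials". The half-life itself is redacted.
- Section 10.4.1 requires male participants to follow the contraception rules for at least 18 weeks after dosing.

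Three other provisions bear on the point. Section 4.4 says "Follow-up visits in addition to those in the SoA may be scheduled at investigator discretion". Section 8.3.1 requires active adverse event collection through a "minimum of the time of the final planned follow-up visit after the administration of the study intervention". Section 8 treats adherence to the schedule as essential.

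**The concern.** A site that works from the dated columns finishes each participant between weeks 14 and 16. No dated visit reaches week 18, and later visits are optional.

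Three things follow:

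- **Safety data.** Adverse event collection must run at least to the final planned visit, and scheduled laboratory tests, vital signs and weight end there too. A safety summary labelled as about 18 weeks would then rest on 14 to 16 weeks of scheduled data.
- **Rationale.** If 18 weeks is the length derived from the half-life, a 15-week schedule may not meet that reasoning, and the last PK sample comes 3 weeks earlier than the text implies.
- **Contraception.** Section 5.3.4 links contraception counselling to the scheduled time points: "the investigator or designee will inform the participant of the need to use highly effective contraception consistently and correctly". The last such contact falls about 3 weeks before the male contraception period ends.

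**Working it through.** **Inputs.** Dosing on Day 1 (protocol Section 4.1). Last dated visit Day 106 ±7 and the one before it Day 93 ±7 (Section 1.3). Screening up to 4 weeks, follow-up about 18 weeks, total about 22 weeks (synopsis, Section 4.1). Eighteen participants (Section 4.1).

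**The plan's own total.** 4 + 18 = 22 weeks, or 28 + 126 = 154 days. The text agrees with itself.

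**The schedule.** Weeks after dose = (study day − 1) / 7.

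| Study day | Days after dose | Weeks after dose |
|---|---|---|
| 99 (earliest for last visit) | 98 | 14.0 |
| 106 (nominal) | 105 | 15.0 |
| 113 (latest for last visit) | 112 | 16.0 |
| 127 | 126 | 18.0 |

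If the day number is instead read as elapsed days, Day 106 is 106 / 7 = 15.1 weeks and Day 113 is 113 / 7 = 16.1 weeks. Neither reading reaches 18.

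**Shortfall.** Nominal: 126 − 105 = 21 days, and 21 / 126 = 16.7%. By window: 126 − 112 = 14 days to 126 − 98 = 28 days, or 11.1% to 22.2%.

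**Total participation under the schedule.** 28 + 105 = 133 days = 19.0 weeks, at most 4 + 16 = 20, against 22 stated.

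**Whole study.** Stated: 18 × 18 = 324 participant-weeks. Scheduled: 18 × 15 = 270. Difference 54; by window 18 × 2 = 36 to 18 × 4 = 72. This is the same gap on another scale.

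**Windows of the last two visits.** 93 + 7 = Day 100 and 106 − 7 = Day 99, so they overlap.

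**Half-life (assumed values only, because the real one is redacted).** Half-lives covered = days / half-life.

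| Assumed half-life (days) | Covered by 105 days | Covered by 126 days |
|---|---|---|
| 21 | 5.0 | 6.0 |
| 25.2 | 4.2 | 5.0 |
| 28 | 3.75 | 4.5 |

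Whether 15 weeks meets a rule such as five half-lives depends on the undisclosed value. The effect on AUCinf and t1/2 cannot be calculated from the documents.

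**The case against.** The arithmetic is not in dispute. The case against giving it weight has five parts.

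- **Damaged table.** In the text copy, the second heading row has lost its Day 1 label, and the row cells do not match the number of headings. A check against the PDF is reasonable. But both heading rows end at Day 106, and the first table has fewer cells (16) than its headings imply (17), so nothing suggests a lost later visit.
- **The footnote is part of the schedule.** It states 18 weeks as the plan, so the final planned visit could be read as week 18. That makes the schedule ambiguous, but it still gives no day, window or list of assessments for a week-18 visit. Section 4.4 only permits extra visits.
- **An easy correction route exists.** Section 8.4 lets assessment timings be changed, or time points added, with documented approval and no amendment. This lowers the cost of correction; it does not schedule anything.
- **No visible analysis needs 18 weeks.** This stands. There are no hypotheses. SAP Section 3.5.1 counts treatment-emergent events up to the end of the study, other summaries are by visit or time, and AUCinf and t1/2 are reported as data permit. The participant-week figure feeds no planned rate.
- **Which figure was intended is not proven.** This also stands. The 22-week total contains the 18 and is not independent evidence. The contraception period is better support, but it does not fix a visit date.

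**Conclusion.** The point holds. The schedule delivers 15.0 weeks of planned follow-up (14 to 16 by window) where the endpoint, design text, footnote and SAP state about 18. A gap of 3 weeks, or 17%, that the latest permitted visit cannot close is more than the word approximately can reasonably cover.

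It should be fixed, but the harm is limited. The study is descriptive, related serious events remain reportable after completion (Section 8.3.1), pregnancies are followed to outcome (Section 8.3.5.1), and the safety data can still be summarized with the correct duration. No effect on the PK results is claimed.

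The conclusion assumes that the two heading rows reproduce the source table correctly. That 18 weeks is the intended figure is likely from its repeated use, but it remains an inference the sponsor must confirm.

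**What to change.** The sponsor should confirm the intended duration against the half-life, then make one of these changes.

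1. **Preferred if 18 weeks is intended: move the last visit to Day 127 ±7.** The window becomes Day 120 to 134, or 119 / 7 = 17 to 133 / 7 = 19 weeks after dose. It opens 120 − 100 = 20 days after the latest Day 93 visit, so the overlap goes. Cost: one column changed and no extra visit or participant. Each participant stays 3 weeks longer than the current schedule but within the stated 22. The drawback is PK sampling: the nominal gap between the last two samples grows from 106 − 93 = 13 days to 127 − 93 = 34 days.
2. **If the Day 106 sample is needed for the terminal phase: keep it and add Day 127 ±7.** Cost: 18 extra visits. Narrow the Day 93 and Day 106 windows, for example to ±3 (93 + 3 = Day 96, before 106 − 3 = Day 103).
3. **If 15 weeks is intended: restate it.** Give about 15 weeks of follow-up and 19 weeks in total in protocol Sections 1.1, 1.3 (footnote), 3, 4.1 and 4.2 and SAP Sections 2.2 and 2.3. Confirm that 15 weeks meets the half-life rationale, narrow the last two windows as above, and keep the 18-week male contraception requirement. Cost: wording in one protocol amendment and one SAP update.

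Section 8.4 may allow the first two without a formal amendment, but the printed schedule should still be corrected.
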